10. OUTCOME MEASURES

10.1 Primary outcome measure:

The IPPoMS trial has an adaptive design that will determine the primary outcome measure for the IPPoMS protocol based on pre-determined analysis of the quantitative clinical and neuroimaging secondary outcome measures in the first 30 subjects who finish 1 year of pre-treatment baseline. This analysis is expected to be concluded in the spring/summer of 2013. The primary outcome measure that comes out of the pre-determined analysis in the IPPoMS trial will be adopted as primary outcome measure in the IPPoMS-E trial.

10.2 Secondary outcome measures:

10.2.1 Neuroimaging outcomes:

1. Inhibition of individualized rates of development of brain atrophy: effect of idebenone on individualized rates of development of brain atrophy
2. Inhibition of individualized rates of development of brain gray matter atrophy: effect of idebenone on individualized rates of development of segmented gray matter atrophy
3. Inhibition of individualized rates of enlargement of ventricular volume: effect of idebenone on individualized rates of enlargement of segmented volume of 3rd ventricle
4. Inhibition of individualized rates of development of cervical SC atrophy: effect of idebenone on individualized rates of development of SC atrophy
5. Inhibition of individualized rates of neuroaxonal destruction as assessed by T1 relaxation time in the brain (ROI in normal appearing white matter and in deep gray matter): effect of idebenone on individualized rates of neuroaxonal destruction

6. Inhibition of individualized rates of neuroaxonal destruction as assessed by T1 relaxation time in the cervical spinal cord: effect of idebenone on individualized rates of neuroaxonal destruction
7. Inhibition of individualized changes in axonal integrity as assessed by axial diffusivity and of changes in myelin integrity as assessed by radial diffusivity on brain DTI imaging: effect of idebenone on individualized rates of neuroaxonal destruction

10.2.2 Clinical/functional outcomes:

1. Progression of lower extremity disability as assessed by 25 foot walk component of MSFC (comparing area under curve (AUC) between 1 year of pre-treatment baseline collected during IPPoMS trial and one year of idebenone therapy)

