2. Progression of upper extremity/fine motor movements disability as assessed by 9 hole peg test component of MSFC (comparing area under curve (AUC) between 1 year of pre-treatment baseline collected during IPPoMS trial and one year of idebenone therapy)
3. Progression of neurological disability as assessed by MSFC (comparing area under curve (AUC) between 1 year of pre-treatment baseline collected during IPPoMS trial and one year of idebenone therapy)
4. Progression of neurological disability as assessed by Scripps NRS (comparing area under curve (AUC) between 1 year of pre-treatment baseline collected during IPPoMS trial and one year of idebenone therapy)
5. Progression of neurological disability as assessed by EDSS (comparing area under curve (AUC) between 1 year of pre-treatment baseline collected during IPPoMS trial and one year of idebenone therapy)

10.2.3 Biological/immunological outcomes:

1. Analysis of changes in CSF albumin quotient (ROS are known to disrupt endothelial tight junctions; which may be measured as increase in CSF albumin quotient)
2. Analysis of changes in CSF biomarkers of oxidative stress and mitochondrial stress (e.g. 4-HNE, DJ-1)
3. Analysis of changes in CSF lactate, as a biomarker of extra-mitochondrial glucose metabolism
4. Analysis of changes in CSF biomarkers of CNS tissue destruction (e.g. NCAM, OMGP and Contactin-2)
5. Analysis of changes in CSF biomarkers of inflammation (e.g. CXCL13, IL-12p40, sCD27)

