11.2 Statistical analyses of outcome measures

Descriptive methods will be used to analyze the safety data. Generally, for the analysis of efficacy data in IPPoMS-E protocol, we will utilize equivalent outcomes collected during IPPoMS trial.

For primary and secondary outcome measures, we will use identical statistical approach as utilized in IPPoMS trial: i.e. in order to utilize all collected data, we will calculate areas under curve (AUC) values for each outcome, normalized per 1 year of “therapy”. Thus, we will calculate AUC for three different “treatments”: pre-treatment baseline (B), placebo (PI) and for idebenone (I) treatment. We will compare intra-individual changes in AUC values by following linear mixed effect model:

$AUC_{\text{outcome}} = \text{treatment (B, PL, I)} + \text{group} + \text{interaction between treatment and group} + \text{covariates}$

where “group” refers to original “placebo” versus “idebenone” groups from IPPoMS trial and the random part is patient. While randomization is stratified for age and therefore, we are expecting that the placebo and active treatment groups will be well-matched for age, we will use Age and sex as covariates in the model if we detect any interaction.

In addition to analysis of primary and secondary outcomes, combining data collected during IPPoMS and IPPoMS-E studies will significantly enhance our ability to detect treatment-related changes in CSF biomarkers. Depending on how many subjects choose to participate in IPPoMS-E, the amount of paired (i.e. no treatment versus idebenone) CSF samples may theoretically increase up to 2 fold in comparison to IPPoMS trial. Therefore, the cohort of patients originally assigned to placebo can be utilized as “confirmatory” cohort for biomarker changes identified in the IPPoMS trial. This would effectively increase the power for detecting significant differences, as only those biomarkers found to be significantly changed during the IPPoMS trial would be tested in the IPPoMS-E trial, thus limiting the number of multiple comparisons that would need to be performed (and for which p values need to be properly adjusted). Again, the differences in selected CSF biomarkers between “no-treatment”, “placebo” and “idebenone” treatment would be analyzed using the same mixed effect model.

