11.3 Handling of missing/unobtainable data

All efforts will be made to collect a complete set of data by employing 2-4 week flexibility in scheduling and repeating inadequate quality MRI scans.

In the event that particular data points are missing for reasons other than inability to perform the test (i.e. because of disability) we will replace the missing data according to following algorithm:

- a. For data obtained every 6 months (i.e. clinical data and brain MRI data), the missing time point will be substituted by the average of 2 adjacent time-points: i.e. 6 months before and 6 months after the missing time-point. If the last time-point is missing (i.e. month 36), we will substitute the data for this time-point by the average of 2 preceding time-points.
- b. For data obtained once at treatment phase (i.e. CSF and apheresis data), the missing data cannot be replaced and the patient will be eliminated from analysis.

Handling data missing because the patient was unable to perform the test due to disability: this may happen for clinical tests such as timed 25 foot walk (25FW), 9 hole peg test (9HPT) and PASAT. These data will be calculated using the following recommendations from scoring instructions for the MSFC:

- a. 25FW: the inability to perform 25FW will be substituted by the largest Z-score in the MSFC Task force database (i.e. with the slowest time of any patient in the combined dataset used by the Task Force in its published meta-analysis). The largest Z-score in the

Task Force dataset is 13.7, therefore, for a subject who could not complete the 25FW Z_{leg} , average = -13.7 will be used.

- b. 9HPT: the inability to perform 9HPT will be coded as 777 and the following Z-score calculation formula will be applied:

$$Z_{arm, trial\#} = [(1/777 - \text{Baseline mean (1/9HPT)}) / \text{Baseline SD (1/9HPT)}]$$

- c. PASAT: In the event an individual patient cannot complete PASAT-3 due to disability, a score of 0 will be assigned.

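### The patient-only mixed model in 11.2 gives period AUCs of unequal precision one variance, so idebenone-versus-baseline tests are miscalibrated in opposite directions: about 9% in ex-placebo and 3.5% in ex-idebenone patients

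*Combined protocol and SAP*

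**What the plan says.** Section 11.2 reduces each patient's data to one AUC per period: "we will calculate areas under curve (AUC) values for each outcome, normalized per 1 year of" therapy. The three periods are "pre-treatment baseline (B), placebo (PI) and for idebenone (I) treatment". These enter a linear mixed model with treatment, original group, their interaction and covariates, in which "the random part is patient". The section names no weights, period-specific variance, residual correlation or random slope. Its stated aim is to use everything collected, with the same approach as the parent trial.

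The periods differ in length. Baseline is one year (10.2.2), placebo two years (3.4), and idebenone one year for patients who had placebo in IPPoMS (ex-placebo). For those who had idebenone (ex-idebenone), 5.2 extends the data to three years in total. For the clinical outcomes, however, 10.2.2 describes "comparing area under curve (AUC) between 1 year of pre-treatment baseline collected during IPPoMS trial and one year of idebenone therapy", without naming a group.

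Section 11.3 gives the spacing: "For data obtained every 6 months (i.e. clinical data and brain MRI data"). Under 7.4 and 7.5.1, the Month 24 IPPoMS visit also serves as the extension baseline.

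**The concern.** An average over seven visits is more precise than one over three, and dividing by duration does not change that. A model with only a patient effect and one residual variance treats all period values as equally precise and equally correlated. Its pooled residual is pulled down by the long periods and then applied to the two shortest, baseline and the ex-placebo idebenone year. Ex-placebo patients are those in whom the extension adds a new off-drug versus on-drug comparison (3.4, 5.2). If their standard error is too small, chance differences are called significant too often. In ex-idebenone patients the error runs the other way.

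A second issue is the window. Month 24 precedes the first open-label dose, yet a trapezoid AUC from Month 24 to 36 counts it as part of the idebenone year.

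**Working it through.** The plan gives no alpha, power or sample-size figure for this test (11.4 calls these not relevant), so there is no stated figure to reproduce.

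**Inputs from the documents:** six-monthly visits (11.3); period lengths as above; a patient-only random part (11.2); 66 expected completers of dosing in the parent trial (11.5).

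**Assumptions:** two-sided 5% test; trapezoid AUC; one residual variance; visits at Months -12 to 36, with Month 0 closing baseline and opening treatment; independent visit errors of variance 1; no mean progression; 33 patients per group in simulations.

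**1. Variance of each AUC** (sum of squared weights)
- 1 year, weights 1/4, 1/2, 1/4: 0.0625 + 0.25 + 0.0625 = 0.375
- 2 years, weights 1/8, three of 1/4, 1/8: 2/64 + 3/16 = 0.219
- 3 years, weights 1/12, five of 1/6, 1/12: 2/144 + 5/36 = 0.153

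**2. Covariance through a shared visit**
- Baseline-placebo and placebo-idebenone (ex-placebo): 1/4 × 1/8 = 0.03125 each
- Baseline-idebenone: 0 in ex-placebo; 1/4 × 1/12 = 0.0208 in ex-idebenone

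**3. True variance of idebenone minus baseline, I - B (per patient)**
- Ex-placebo: 0.375 + 0.375 = 0.750
- Ex-idebenone: 0.375 + 0.153 - 2 × 0.0208 = 0.486

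**4. What the model assigns.** Within each group the residual is the mean variance minus the mean covariance.
- Ex-placebo: (0.375 + 0.219 + 0.375)/3 - 0.0625/3 = 0.3021
- Ex-idebenone: (0.375 + 0.153)/2 - 0.0208 = 0.2431
- Pooled (2 and 1 df per patient): (2 × 0.3021 + 0.2431)/3 = 0.2824
- Model variance of I - B in both groups: 2 × 0.2824 = 0.565

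**5. Size** = 2[1 - Φ(1.96 × √(model variance / true variance))]

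| Contrast | Model | True | SE ratio | Size | REML simulation |
|---|---|---|---|---|---|
| Ex-placebo | 0.565 | 0.750 | 0.87 | 8.9% | 8.4-9.0% |
| Ex-idebenone | 0.565 | 0.486 | 1.08 | 3.5% | 3.5-3.6% |
| Equal-weight average | 0.282 | 0.309 | 0.96 | 6.1% | 5.5-6.0% |

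The average row uses (0.750 + 0.486)/4 and 2 × 0.565/4. Each simulation scenario had 4,000 runs.

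**6. One idebenone year in both groups.** Section 10.2.2 does not say which year; the check took Months 24-36. The ex-idebenone residual becomes 0.375, the pooled residual (2 × 0.3021 + 0.375)/3 = 0.3264 and the model variance 0.653, against a true 0.750 in each group. Size is 6.8% for every contrast.

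**7. Other error structures**

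| Structure | Ex-placebo | Ex-idebenone | Average |
|---|---|---|---|
| AR(1), six-month correlation 0.3-0.9 | 9.6-13.7% | 3.5-3.8% | 6.5-8.7% |
| Between-patient slope SD 0.1-1.0 visit SD per year | 9.5-16.5% | 3.5-4.1% | 6.4-10.4% |

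The ex-placebo limit when slope differences dominate is 17.4%.

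**8. Role of the shared visits.** With no sharing and variances in the ratio 1 : 1/2 : 1/3, the group residuals are 0.833 and 0.667, pooled 0.778. The model variance is 1.556 against a true 2 in ex-placebo patients, a size of 8.4%. Sharing therefore accounts for about half a percentage point of the 8.9%.

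**9. Dilution.** Month 24 has weight 1/4 in the ex-placebo idebenone year, so an immediate constant effect S reads as 0.75 S. If Month 0 opens the ex-idebenone AUC, the same effect reads there as (1 - 1/12) S, about 0.92 S.

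**The case against.** The strongest reply is that no single miscalibrated test can be identified. Section 11.2 does not say which I-versus-B contrast is tested, and no alpha is given for any efficacy test. A reader might infer that the comparison with baseline generally runs at 7-9%, or that 10.2.2 singles out ex-placebo patients. Neither is supported. The ex-idebenone contrast is conservative, the average is about 6% with independent errors, and 10.2.2 names no group.

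A reader might also take one residual variance as stated text, or the shared switch visits as the main cause. The first is only the default reading; the plan borrows the parent trial's approach, and that protocol is not available here. The second fails on step 8: in ex-placebo patients baseline and the idebenone year share no visit at all.

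The null used here is also unrealistic. Section 4.1 describes primary progressive disease as worsening from onset, and baseline precedes idebenone in every patient. No covariance structure repairs that. Finally, this is an open-label extension with no power basis, and 7.6.1 stops it for futility, so no confirmatory decision rests on the p-value.

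These points limit the claim and its weight. They leave the defect standing: the model as written, fitted in the usual way, gives wrong standard errors. Section 7.6.1 moves the data to the natural history protocol for further analysis, so the model may still be used. The protocol's own references to patient-specific slopes (3.4) and individualized rates (10.2.1) make independent errors the favourable case for the ex-placebo contrast.

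**Conclusion.** The concern holds in a limited form. Under the default reading, the I-versus-B contrast gets the same variance in both groups when the true variances differ. With independent visit errors, the ex-placebo standard error is about 13% too small (size about 9%) and the ex-idebenone one about 8% too large (size about 3.5%). The equal-weight average runs at about 6%. With one idebenone year in both groups, size is about 7%. Serial correlation or slope differences take the ex-placebo contrast to roughly 10-17%.

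Unequal period length, and correlation that falls as periods lie further apart, drive the error. All figures rest on the assumptions listed in the working, chiefly a 5% two-sided test, the trapezoid rule, one residual variance and no mean progression. The dilution to 0.75 S is a separate matter and applies only to an immediate, constant effect; 11.2 also contemplates an effect that builds over time.

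**What to change.** Keep the AUC approach and change the wording of 11.2:

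- Estimate the period covariance without structure and separately by original group, or use a paired within-patient test for each named contrast. In 20,000 simulations per scenario (slope SD 0, 0.3 and 0.5 visit SD per year), estimating the variance of I - B from each group's own differences gave sizes of 4.8-5.1% for both groups and their average.
- State which I-versus-B contrast is tested (ex-placebo, ex-idebenone or a defined average) and at what alpha.
- Reconcile the use of all data in 11.2 with the single idebenone year in 10.2.2.
- Treat Month 24 as a pre-dose value, outside the ex-placebo idebenone AUC.

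The cost is small. The covariance needs 6 parameters for three ex-placebo periods and 3 for two ex-idebenone periods, 9 against 2 now, with slightly fewer degrees of freedom. Dropping Month 24 leaves Months 30 and 36; their simple mean has variance 1/4 + 1/4 = 0.5 instead of 0.375, but carries S rather than 0.75 S. An unstructured covariance over all nine visits would need 9 × 10/2 = 45 parameters with perhaps 66 patients or fewer, and is not recommended.

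None of this removes the confounding of idebenone versus baseline with natural progression, which the report should state.

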Finally, combining CSF data from IPPoMS with IPPoMS-E will provide two different longitudinal datasets: for patients originally randomized to placebo, we will have three CSF samples off therapy (Mo -1: baseline, Mo 12&24: placebo) and for patients originally randomized to idebenone, we will have three CSF samples (Mo12, 24 and 36). These longitudinal data will allow us to calculate “slope” of progression and compare these slopes between two different treatments using again linear mixed model:

$\text{Biomarker} = \text{time} + \text{treatment} + \text{interaction between time \& treatment} + \text{covariate}$

where “treatment” is either idebenone or no idebenone (i.e. pre-treatment baseline + placebo). The interaction between treatment and time will assess if the slopes for two treatments are parallel or not. It has been suggested that evaluating changes in the “slope” of progression may distinguish true ongoing neuroprotective effect from static “symptomatic” effect (*Machado, Murray et al. 1999; Ginsberg 2008*). In other words, under hypothetical scenario that idebenone may prove efficacious in PP-MS, its effect on disability may vary depending on the pathophysiology of the disease. There are two possible scenarios:

1. That idebenone enhances ATP production in neurons, soon after initiation of its dosing, and this enhances electrical conduction in demyelinated axons. The result would be improvement in neurological function. However, if enhancement of ATP production does not also lead to neuroprotection, then the “slope” of progression after initiation of idebenone therapy would be parallel to the “slope” of progression off therapy. In other words, the efficacy on the outcome would be “static” – resetting the baseline, but not changing the “slope” (Figure 3A).
2. That idebenone enhances ATP production in neurons, oligodendrocytes and astrocytes. This may, to some degree, protect all CNS cells from death. As death of neurons and oligodendrocytes continues on a progressive basis, a true neuroprotective drug will inhibit

the slope of the measured outcome (e.g. progression of disability or CNS tissue destruction) in comparison to no treatment. Such dynamic effect would lead to a greater absolute difference in the outcome with greater duration of therapy (Figure 3B). Finally, the drug may have both symptomatic and neuroprotective effects (Figure 3C).

[figure not shown]

Figure 3:

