Possible effects on the outcome (e.g. disability) by static “symptomatic” versus true “neuroprotective” therapeutic

- A. Static “symptomatic” effect will “reset the baseline” but will not alter the slope of progression
- B. True neuroprotective drug will change the slope of progression, so its efficacy on the outcome (i.e. the absolute difference in comparison to no treatment condition) will increase with the duration of treatment
- C. Combination of static and dynamic effect on the outcome by therapeutic that has both symptomatic and neuroprotective effect

Based on this rationale, for CSF biomarkers of CNS tissue destruction (that may be changing in time), we will evaluate the slopes of the change between idebenone and no idebenone treatments.

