11.4 Power analysis and sample size calculation

Sample size and power considerations are not relevant here as this is an open-label extension study design.

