11.5 Accrual number request

Because up to 85 patients can be enrolled into IPPoMS study (to yield 66 subjects who complete 2 years of dosing), theoretically up to 85 subjects can be enrolled into IPPoMS-E study.

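### The plan's only route to calling CSF biomarker slopes parallel is a non-significant interaction, which cannot show parallelism and fits no effect equally well

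*Combined protocol and SAP*

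**What the plan says.** Section 11.2 describes a linear mixed model for CSF biomarkers with time, treatment, their interaction and a covariate. Treatment means idebenone versus no idebenone. Of the interaction it says: "The interaction between treatment and time will assess if the slopes for two treatments are parallel or not".

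Two scenarios give the answer a meaning. In the first (Figure 3A), idebenone improves conduction without protecting cells, "resetting the baseline, but not changing the" slope; the figure legend says such an effect "will not alter the slope of progression". In the second (Figure 3B), a neuroprotective drug changes the slope. Figure 3C combines both. The text is hedged: comparing slopes "may distinguish true ongoing neuroprotective effect from static" effects, under the hypothetical that idebenone proves efficacious.

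The commitment that follows is limited: "for CSF biomarkers of CNS tissue destruction (that may be changing in time), we will evaluate the slopes of the change". Primary and secondary outcomes otherwise use the AUC model earlier in the same section.

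Section 4.7 says this kind of modelling may either support or contest a neuroprotective effect. Section 11.4 sets power aside: "Sample size and power considerations are not relevant here as this is an open-label extension study design". No significance level, margin, interval rule or handling of a null interaction appears.

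**The concern.** Parallel is a claim of equivalence between two slopes. A test whose null hypothesis is zero interaction can give evidence that slopes differ, but failing to reject does not show that they are the same. Because section 11.2 asks for a two-way answer and offers no other criterion, a non-significant result is the only thing that could lead to parallel.

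There is a second gap. In the plan's own scenarios a static effect has two parts: a shift in level and an unchanged slope. A null interaction speaks only to the second part, and imprecisely, so it cannot separate a static effect from no effect.

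At stake is the secondary goal on mechanism of action (section 5.2). Section 4.7 expects the modelling to count against neuroprotection as well as for it, so an imprecise null could be reported as evidence about mechanism when it mainly reflects sample size. The issue survives the early stop, because section 7.6.1 transfers data and samples to protocol 09-N-0032 for further analysis.

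**Working it through.** The plan gives no power figure to reproduce, so the question is how informative a non-significant interaction would be.

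**Inputs from the documents**
- Three CSF samples per patient: months -1, 12 and 24 for the original placebo arm; months 12, 24 and 36 for the original idebenone arm (section 11.2).
- The month 24 lumbar puncture is done under the extension (section 7.5.1), so both arms are limited to patients who enter it.
- Number of patients: section 11.5 gives a theoretical maximum of 85, expected "to yield 66 subjects who complete 2 years of dosing".

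**Assumptions (not in the documents)**
- Two-sided 5% test.
- Equal arms. The statement in section 11.2 that paired samples could rise up to two-fold suggests this but does not state it.
- True slope difference d, in units of the between-patient SD of fitted slopes; 0.5 is used as the reference value.

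**Miss rate.** Treat the interaction as a two-group comparison of patient slopes with n per arm. The standard error is sqrt(2/n) SD, and the t statistic is noncentral with noncentrality d / sqrt(2/n) on 2n - 2 degrees of freedom. At n = 33, sqrt(2/33) = 0.246, so d = 0.5 gives noncentrality 0.5/0.246 = 2.03 against a critical value of 2.00. Power is therefore only just above one half.

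| Per arm | Miss rate at 0.3 SD | at 0.5 SD | at 0.8 SD |
|---|---|---|---|
| 33 (66 completers) | 78% | 48% | 11% |
| 42 (about 85) | 73% | 38% | 5% |
| 20 (illustrative) | 85% | 66% | 31% |

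About 64 per arm would be needed for a 20% miss rate at 0.5 SD. A one-sided 5% test would lower the 0.5-SD miss rate to about 35% at 33 per arm and 25% at the maximum (normal approximation).

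**Interval width.** At 33 per arm the 95% half-width is 2.00 x 0.246 = 0.49 SD. An estimated difference of exactly zero would still be compatible with differences of about half an SD in either direction.

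**Why usable numbers may be smaller**
- Entry requires completing the parent study (section 6.2), so 85 is theoretical.
- Section 4.7 expects some patients to decline.
- Section 11.3 eliminates patients with missing CSF data.
- Enrolment closed early (section 7.6.1), and the final visit lists no lumbar puncture (section 7.6.1, Appendix A). Anyone stopped before month 36 therefore lacks the third on-idebenone sample.

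The resulting numbers are not given. As illustrations, 33 off-drug against 20 on-drug patients gives a 59% miss rate at 0.5 SD, and 33 against 15 gives 65%.

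**The case against.** The strongest reply is that the plan contains no rule equating a non-significant p-value with parallel slopes. Saying that an interaction assesses parallelism is an ordinary description of the term, the scenarios reason from mechanism to expected slope and not from test result to mechanism, and the language is conditional. This stands. A reader might infer that the plan commits to declaring a static effect on a null test, or that a drug which does change the slope would be called static about as often as it was detected. The documents support neither. No such sentence exists, and their own account of a static effect also requires efficacy and a reset level. What remains is that no other route to parallel is offered.

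It is also fair that the 48% and 38% depend on assumed inputs; the table shows how far they move with the effect size. They must be read as conditional.

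Finally, section 7.6.1 reports that the parent trial found no significant efficacy, so the premise behind the static-versus-neuroprotective question was not met and the practical consequence is reduced. That is true, but analysis of the data and samples continues. After a null parent trial and an early stop, a non-significant interaction is a plausible result, so its interpretation still needs settling.

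**Conclusion.** The concern holds as a gap in the decision rule. Section 11.2 asks a test of zero interaction to say whether slopes are parallel and attaches a mechanism to that answer, without a margin, an interval criterion or an inconclusive outcome.

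With two-sided 5% testing, equal arms and a 0.5-SD difference, all assumed, a real slope difference is missed about 48% of the time at the 66 expected completers and 38% at the theoretical maximum. At 33 per arm the rate runs from about 11% at 0.8 SD to 78% at 0.3 SD. Attrition and the early closure would push it up.

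The scope is limited to the slope analysis of CSF tissue-destruction biomarkers, which serves the mechanism goal. The AUC analyses of primary and secondary outcomes are not affected. The change is worth making, but it does not undermine the study's main analyses.

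**What to change.** Amend section 11.2 as follows:

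1. Report the slope difference with its 95% confidence interval for every biomarker analysed this way.
2. State that a non-significant interaction is inconclusive about slope.
3. Claim parallel slopes only if the 90% interval lies wholly within a stated margin. Fix the margin before the CSF slope analysis is run; since section 7.6.1 reports the parent trial as already analysed, a deadline tied to unblinding would be out of date.
4. Use the term static only if a level shift (the treatment main effect) is also shown. State the time origin at which that shift is estimated, because the main effect depends on it once an interaction is in the model.
5. Otherwise report the result as indeterminate.

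The change is to wording only and needs no new data. The price is frequent indeterminate results. With an illustrative margin of 0.5 SD and truly equal slopes, parallelism would be reached about 29% of the time at 33 per arm and 47% at 42. These figures apply to that margin only. The 90% half-width at 33 per arm is 1.67 x 0.246 = 0.41 SD, so a margin below about 0.41 SD could seldom be met. That is a limit of the sample, which the present rule leaves out of sight.
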